mailed. Patients will be called up to 6 times at different times of the day to make contact. Once contacted, research coordinator (RC) will confirm eligibility and obtain verbal consent to study procedures. For consenting patients. RC will administer the baseline survey and verbally consent them to participation in the VA "Annie" program and motivational texting program. Documentation of verbal consent to Annie participation is required by the VA Office of Connected Care. Annie consent language has been approved by MVAHCS representative ([name], MvHealtheVet coordinator). Verbal consent will be documented in CPRS in a Research Participant Note utilizing the "Annie Consent"

Figure 1: Study flow diagram of the randomized pilot evaluation

template. Patients who decline to complete baseline and immediately have care coordination will be considered ineligible. PCP and PACT pharmacist will be notified by co-signature to a research participant note.

Baseline Assessment:

Phone survey will assess: current tobacco use, motivation to quit, prior quit experiences, use of technology, and severity of shortness of breath. See table of measures. Charlson comorbidity index and history of mental health diagnoses will be pulled from the CDW.

Annie Enrollment:

All consenting participants will be enrolled in the VA "Annie App" and will receive an initial text message informing them of this enrollment. The Annie App is the VA's text-message-based health promotion platform used to provide education, self-management and clinical protocols. Participants will need to reply once to this message to confirm enrollment. Participants already enrolled in the Annie App will have this participation confirmed in the Annie portal.

Randomization:

Consenting participants will be randomized 2:1 to the intervention versus usual care using the enrollment application. To maintain balance in race and gender, randomization will be stratified by these characteristics; within strata, randomization will employ randomly permuted balanced blocks of size 2, 4, and 6.

Proactive Protocol V2.1 11/20/23

Usual Care:

Participants in the usual care arm will be managed per usual as directed by their medical team.

Intervention:

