Participants randomized to the intervention will be enrolled in a longitudinal motivational text-messaging program designed to increase quit attempts and participation in tobacco treatment. In collaboration with the MVAHCS Annie representative, the motivational protocol was adapted from a nationally available protocol available to all clinicians in the Annie App. Tailoring of the content included the addition of COPD-specific motivational quotations and information, inclusion of the local number to contact the study team, as well as the option for a "call back" from the team.

The Annie protocol will deliver approximately 30 motivational messages and a weekly "check in" over a 12 week period. The program will initially text participants once daily for 2 weeks, then approximately once every three days for 4 weeks, then every week until 12 weeks. Participants can opt out at any time from Annie by texting "stop" or by calling the study team to be discharged from the protocol. Protocol will encourage participants to call the study team to connect them to evidence-based tobacco cessation treatments or to call the VA quitline.

Care Coordination:

All treatments offered are standard of care within the VA and are offered in the context of routine clinical care. Study number is a secure VA number with voicemail that will be monitored. Participants who call back or request a call back via the Annie App will receive a return phone call as soon as possible, within a week. Request for callback and date will be logged in study log. For those participants who indicates a readiness to quit but do not call either the study team or their primary care physician, a study team member will call the participant when they are next monitoring participants within the Annie Program.

Both PI and RC are trained in motivational interviewing. At least 6 attempts will be made to return all calls at different times of the day. If participants are unable to be reached after 6 attempts, a letter will be sent encouraging them to call back, to call the quitline, or to contact their primary care provider.

Participants will be encouraged to enroll in an available MVAHCS quit program that provides both counseling and medication management. Phone script will encourage enrollment in more intensive programs first. Offered programs will include:

- Primary Care/Mental Health integration (PMCI) tobacco cessation management (if enrolled in mental health)

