- Tobacco cessation class with pharmacist co-management
- Pharmacist tobacco clinic
- Quitline with primary care or pharmacist medication management
- Stay Quit Coach App or SmokeFreeVet texting (VA tobacco treatment programs) and primary care medication management

For participants still unwilling to enroll in treatment, they will be offered a stress relief program and can request a one-time callback in a month.

Once the participant has elected which program they would prefer, study staff will place the appropriate referral within CPRS, addending the research participant note to document the selection and discharging the participant from the Annie protocol.

- Pharmacist: Direct co-signature to PACT pharmacist in CPRS
- Cessation class or PCMI: notification to [name], tobacco lead clinician
- Quitline + primary care medication management: notification to [name] (Tobacco Lead Clinician)+ documentation that patient consents to guitline call + co-signature notifying PCP
- Direct enrollment in SmokeFreeVet on smokefree.gov website
- Assistance with downloading of StayQuit Coach

Patients who select to enroll in treatment will be called in approximately a month to ensure they have connected with care and have no further questions.

Final Survey, Biochemical Confirmation of Abstinence, and Qualitative Assessment:

Survey: All participants will be surveyed 6 months after randomization to determine participation in any tobacco treatment (primary outcome), current self-reported tobacco use, quit attempts, and acceptability and feedback of the texting program. Completion via phone will be prioritized but participants will be provided the option to complete the survey via Qualtrics link via email or paper copy. Participants will be contacted 3 times via phone. If they are unable to be reached, they will be sent a letter encouraging them to call the study team to complete the survey.

EHR: Data will be pulled from the CDW supplemented by limited chart review to identify: prescriptions for tobacco-cessation medications, tobacco-treatment-related visits. Tobacco treatment visits will be identified by combining ICD-10 codes for tobacco use and treatment with note titles and visit types for pharmacists, psychologists, and primary care providers.

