Cost Analysis: We will prospectively capture information on cost associated with performing the proactive tobacco treatment intervention. To estimate the cost associated with implementation, we will capture time spent building any templates and electronic tools, and training staff. To estimate cost associated with staffing the program once it is created, for one month during the pilot, all study staff will enter daily the time spent in the clinical tasks associated with delivering the intervention into a spreadsheet, excluding activities that are related only to research administration. To estimate cost related to an increase in use of tobacco treatments attributable to the program, we will estimate the difference in use of tobacco treatments in addition to the intervention-related costs.

Measurements and Data Source:

See Table 1 for full list of measurements and data sources.

Table 1: Measures	
Measures	
Baseline Measures	
Survey	Demographics: Age, gender, race, ethnicity, education, income, health literacy Health Measures: Self-reported health, respiratory symptoms questionaire, diagnosis of COPD, Audit-C Access to Technology: Access to devices, access to internet, use of e-mail, use of secure patient portal, frequency of texting, electronic health literacy scale Tobacco Measures: current tobacco product use, heaviness of smoking index, past-year quit attempts and use of cessation resources, ever use of cessation resources, quit confidence scale, motivation to quit, intention to quit

EHR	Charlson comorbidity index, mental health diagnoses	
Outcome Measures		
Study Recorded and EHR	Response to the program (via telephone, via Annie App), timing of response to program, Acceptance of referral, choice of referral program, cessation medications (varenicline, bupropion,	
ENK	nicotine replacement single/combination), documented tobacco treatment visits (pharmacist, class, mental health, primary care) or warm handoff to quitline	
Survey	Primary outcome: Use of any tobacco treatment	
	Secondary Outcomes: Use of combination treatment (behavioral + pharmacotherapy), individual	
	treatment choice (program, medications), heaviness of smoking, quit attempts (y/n and number),	
	7 day and 30 day abstinence, Stage of change, quit confidence	
	Additional Outcomes: Acceptability of text messaging program, feedback on messages,	
	agreement to qualitative interview	

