A sample size of approximately 167 participants in the intervention arm will be sufficient to estimate rates of contact, referral, and enrollment in behavioral and pharmacologic treatment with a precision (standard error) of +/- 3.9% and the control arm of 5.4%, which will be informative for planning future research. However, if feasible we will continue recruitment to attain more precision. Similarly, we will be able to estimate eligible population sizes, outreach connection rates, referral rates, rates of behavioral treatment enrollment and rates of pharmacologic treatment separately, and related facets of the intervention delivery to within similar degrees of precision. We will have enough variation in patient characteristics to stratify uptake on key variables, including age and disease severity. We may not have sufficient power to determine a statistically significant increase in enrollment in behavioral and pharmacologic treatment or smoking cessation, but these will be examined as aims of future research.

Cost Analysis: Estimates of time and workload for each staff member and clinical role involved in implementing and staffing the program will be combined with regional VA salary information to generate total costs for the proactive program. We will combine this also with regional estimates of pharmacy costs and the prevalence of

COPD and tobacco use at the MVAHCS to produce an overall estimate of cost for the program should it be implemented for the total population.

Qualitative Analysis: Transcribed interviews and notes will be analyzed using directed content analysis with NVIVO software, with constructs based on the technology adoption model and the consolidated framework for implementation research.

Expected Outcomes and Deliverables:

We expect that an electronic proactive patient engagement program will be feasible and will result in more patients enrolling in tobacco treatment. We also expect variation in response to the program by age and baseline technology use. We expect to find that the budget impact of the intervention itself is small and that most of the increase in cost will be due to increased utilization of existing quit resources.

Informed Consent

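### The 6-month survey that supplies the primary outcome gets 3 phone attempts where the protocol elsewhere uses 6 at varied times; raising it to 6 is a cheap improvement

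*Combined protocol and SAP*

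**What the plan says.** The protocol sets three calling rules.

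- Recruitment: "Patients will be called up to 6 times at different times of the day to make contact".
- Call-backs under Care Coordination: "At least 6 attempts will be made to return all calls at different times of the day".
- The 6-month survey, under Final Survey, Biochemical Confirmation of Abstinence, and Qualitative Assessment: "Participants will be contacted 3 times via phone". No varied-times rule is attached.

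Table 1 has "Primary outcome: Use of any tobacco treatment" in its Survey row. The same row holds quit attempts, 7-day and 30-day abstinence, and acceptability of the texting program.

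The three calls are not the whole follow-up effort. Phone is the preferred mode, but "participants will be provided the option to complete the survey via Qualtrics link via email or paper copy". After failed contact: "If they are unable to be reached, they will be sent a letter encouraging them to call the study team to complete the survey". Under Subject Compensation, the payment for both surveys (USD 40) is made when the follow-up survey is completed. Cessation prescriptions and tobacco-treatment visits are also extracted from the EHR.

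On precision, the Power and Sample Size section says that about 167 intervention participants allow rates to be estimated "with a precision (standard error) of +/- 3.9% and the control arm of 5.4" per cent. It makes no allowance for non-response, and the Analysis Plan has no rule for a missing survey.

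**The concern.** The protocol twice treats six calls at varied times as the effort needed to reach these patients, yet uses half that number for the survey behind its primary outcome, without giving a reason. A participant first reached on a fourth, fifth or sixth recruitment call was enrolled by a procedure that follow-up does not repeat.

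Two things are at stake. Missing surveys widen the intervals around treatment rates, which the precision statement computes as if everyone responded. Missing surveys can also bias those rates if response is related to treatment use. Contact with the study before the survey differs by arm: intervention participants may have call-backs, calls after signalling readiness to quit, and a call about a month after choosing treatment, while usual care has none of these. Estimating an effect size is part of the first study objective, so a bias here would carry into planning of the larger trial.

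**Working it through.** **Inputs from the protocol.** Up to 250 randomised 2:1; about 167 in the intervention arm; control 250 − 167 = 83 (derived); stated standard errors 3.9% and 5.4%. The documents give no follow-up rate and no per-call contact rate, so every response figure below is an assumption.

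**1. Reproduce the stated precision.** SE = √(p(1 − p)/n) at p = 0.5 with full response:

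- Intervention: √(0.25/167) = 3.87%, stated 3.9%.
- Control: √(0.25/83) = 5.49%, stated 5.4% (a match if truncated; the difference is immaterial).

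The stated figures therefore use all randomised patients at the least favourable rate.

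**2. Allow for survey loss.** Replace n by n × (1 − loss), keeping p = 0.5:

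| Assumed loss | Intervention SE | Control SE |
|---|---|---|
| 0% | 3.87% | 5.49% |
| 10% | 4.08% | 5.79% |
| 20% | 4.33% | 6.14% |
| 30% | 4.62% | 6.56% |

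At 20% loss the 95% half-widths (1.96 × SE) go from 7.6 to 8.5 points and from 10.8 to 12.0 points. Restoring the full-response precision by enrolment would take 167/0.8 ≈ 209 plus 83/0.8 ≈ 104, or 313 patients against a ceiling of 250.

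**3. Check the same loss at a lower rate.** With 30% loss (n about 117 and 58) and a treatment rate of 20%: √(0.16/117) = 3.70% and √(0.16/58) = 5.25%. Both are still within the stated figures.

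**4. Bias from non-response related to treatment use.** Observed rate = p·r₁ / (p·r₁ + (1 − p)·r₀), where r₁ and r₀ are the response rates of treated and untreated participants. With p = 0.30:

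- r₁ = 0.90, r₀ = 0.70: 0.27/(0.27 + 0.49) = 0.27/0.76 = 35.5%, a bias of +5.5 points.
- r₁ = 0.90, r₀ = 0.80: 0.27/(0.27 + 0.56) = 0.27/0.83 = 32.5%, a bias of +2.5 points.

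If the pattern occurred in one arm only, the between-arm difference would be off by the same amount.

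**5. What three more calls could do.** With independent calls and contact chance a per call, the share unreached by phone is (1 − a)³ after three calls and (1 − a)⁶ after six:

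| Assumed a | After 3 calls | After 6 calls |
|---|---|---|
| 20% | 51% | 26% |
| 30% | 34% | 12% |
| 40% | 22% | 5% |
| 50% | 13% | 2% |

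This is phone reach alone, not survey response. Email, paper and letter replies would add to both columns. If people differ in how reachable they are, the gain from calls four to six is smaller than shown.

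**6. Extra calls at a = 25%.** 250 × 0.75³ × (1 + 0.75 + 0.75²) = 250 × 0.4219 × 2.3125 ≈ 244.

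**The case against.** The strongest reply is that counting calls understates the follow-up effort. The survey can be done by email link or on paper, a letter follows failed calls, payment depends on completion, and in month 5 staff check payment paperwork with no restriction by arm. Everyone randomised has already answered a study call. EHR data capture prescriptions and treatment visits without the survey. Recruitment, call-backs and a survey of consented participants also serve different purposes.

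Much of this stands, and it limits the size of the point. It does not remove it. The protocol does not say that the letter carries the link or the paper copy; it asks the participant to phone in. EHR extraction need not capture over-the-counter products, app or texting programs, or treatment outside the VA, although the study itself refers people to a cessation app and a texting program. No section says that EHR data may stand in for a missing survey. Quit attempts and abstinence have no EHR source in Table 1, and carbon monoxide confirmation is triggered only by a survey report of abstinence. Interviews add views on acceptability, but only from a purposive sample.

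A reader might infer more than the documents support:

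- That the stated precision will be missed. No response rate is given, the stated figures are the worst case over p, and step 3 shows a 30% loss that stays within them. The precision statement also covers contact and referral, which are study-recorded and do not depend on the survey.
- That people who needed four to six recruitment calls will be lost. Nothing in the documents shows this, and under the independent-call model the recruitment call count predicts nothing.
- That 30% missing could move an arm's rate by 30 points. That needs an observed rate of 0% or 100%. At an observed 30% with 70% response, the bounds are 0.7 × 30% = 21% and 21% + 30% = 51%, or −9 and +21 points, and EHR data would narrow them.
- That six calls would remove differential non-response. They would reduce missing data but not an arm difference caused by the intervention contacts themselves.

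**Conclusion.** The point holds as a cheap improvement. The primary-outcome survey has half the phone attempts used elsewhere in the protocol and no varied-times rule, and the fallbacks soften the loss without replacing the survey. The precision cost is modest for a pilot with no power target: at 20% assumed loss, about 0.5 points of standard error in the intervention arm and 0.7 in the control arm, at worst-case p and for survey-based rates only. Bias of a few points is possible and may matter more, but its size rests entirely on assumed response rates. How much of the loss three more calls would prevent cannot be derived from the documents.

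**What to change.** Amend the 6-month survey rule to up to 6 phone attempts at different times of day, identical in both arms. After failed contact, send the letter together with the Qualtrics link and a paper copy. Report survey response by arm. Add to the Analysis Plan a sensitivity analysis of the primary outcome that uses EHR treatment data for participants with a missing survey, noting that EHR data may miss over-the-counter, app-based and non-VA treatment.

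The cost is a short amendment, coordinator time (about 240 extra calls over the study at an assumed 25% contact chance per call) and slightly more participant burden. No new procedure is needed, since the protocol already works to this standard at recruitment and for call-backs.

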Population and Setting: We will randomize up to 250 MVAHCS patients in a ratio of 2:1 intervention: control. Inclusion Criteria (EHR):

- 1) Adults >=18 participating in care, defined as a primary care or pulmonary visit within the past 2 years.
- 2) Past-year smoking status in the electronic health record defined by health factors indicating current smoking (Via validated VA algorithm)
- 3) ICD-10 diagnoses of COPD within the past 2 years
- 4) Not already enrolled in VA tobacco treatment (pharmacist treatment, tobacco groups, mental health tobacco treatment). Patients taking only tobacco cessation medications without counseling will be included.
- 5) Not enrolled in hospice
- 6) No diagnosis of advanced dementia

Exclusions (phone eligibility assessment):

- 1) Unable to communicate by phone in English
- 2) No text-capable phone
- 3) Already guit smoking
- 4) Already participating in tobacco treatment program (note: if using OTC meds without counseling, will not be excluded)
- 5) Decline to be in study but would prefer to receive care coordination immediately

Eligibility, Sampling and Recruitment: We will screen and enroll patients who meet the eligibility criteria, applying the above criteria initially using the EHR, confirming criteria during phone contact. Patients will be randomized irrespective of their intention to quit smoking.

Women and Racial Minorities: To increase representation of these groups, we will oversample eligible women and racial/ethnic minority patients with a goal of 14% female patients and 24% minority patients invited to participate.

Study Procedures:

[figure not shown]
Screening: Research coordinator will screen patients for possible eligibility using a secure electronic application located behind the VA firewall.

Invitation: Study is minimal risk and will be conducted under a waiver of HIPPA and documentation of informed consent. Eligible participants will be sent an "opt out" letter that describes the study and contains the necessary elements of informed consent. Eligible patients will have the opportunity to opt out at this time by calling the study team.

Recruitment: Patients will be recruited by phone starting 1 week after letter is

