Annie App	Opted out (y/n), number of messages received, Participant responses received through the app	
Cost Measures		
Staff recorded	Program-associated costs: hours/week for patient identification, number of weekly phone calls,	
	average call duration, time spent coordinating care, technology costs (patient identification	
	queries, development of eligibility app)	
	Treatment-associated costs : medication costs, pharmacy processing costs, average number, type	
	and duration of counseling visits (groups, quitline, pharmacist counseling, tobacco-related primary	
	care visits, mental health treatment)	
Abbas detisas CODD	-phronia abatruativa nulmanary diagga. EUD: Electronia Haalth Boord	

Abbreviations: COPD=chronic obstructive pulmonary disease, EHR: Electronic Health Record

Analysis Plan:

We will perform descriptive analysis of the demographic and health history measures to describe the participants in the study overall, and in each study arm, as well as by outreach contact and receipt of any treatment and combination behavioral and pharmacological treatment. We will also summarize these measures by gender and race. Our primary aim is to assess the feasibility of implementing a larger trial of the electronic patient engagement intervention. Our primary focus then will be estimating rates, along with 95% confidence intervals, of outreach contact and treatment referral in the text outreach arm and of receipt of any and combination behavioral and pharmacological treatment in each study arm; additional analyses will weight observations by sample inclusion probabilities according to gender and race so that sample results are reflective of the overall population. While the study is not powered for detecting differences in cessation, we will explore potential differences in cessation between the two arms using likelihood ratio chi-square tests.

In addition to the descriptive information on the composition of the study population, we will identify the characteristics of those who respond, receive cessation treatment and those who attain abstinence in each arm, again assessing significance of differences in outcomes using logistics regression analyses and likelihood ratio chi-squared tests. This information will be valuable for planning a future study comparing the electronic proactive outreach intervention with previous studies of phone outreach. We will also descriptively analyze the Annie data to further tailor the protocol.

Power and Sample Size:

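### The supplementary weighted analyses name the inclusion probability, not its inverse, as the weight, and leave the target population and the stage of inclusion undefined

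*Combined protocol and SAP*

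**What the plan says.** The Analysis Plan makes estimated rates with 95% confidence intervals its main focus. It then adds that "additional analyses will weight observations" by a stated rule. The rule is to "weight observations by sample inclusion probabilities according to gender and race", and its purpose is given in the same sentence: "so that sample results are reflective of the overall population". No formula, numeric probability or definition of that population follows, and neither *inverse* nor *reciprocal* appears.

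The weighting is needed because of the paragraph on women and racial minorities under Research Design and Methods: "we will oversample eligible women and racial/ethnic minority patients with a goal of 14% female patients and 24% minority patients invited to participate".

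Several steps lie between invitation and analysis:

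- Opt-out after the letter: "Eligible patients will have the opportunity to opt out at this time by calling the study team".
- Contact: "Patients will be called up to 6 times at different times of the day to make contact".
- Phone eligibility, with exclusions that include "No text-capable phone".
- Verbal consent.
- For survey outcomes, response at 6 months. Table 1 lists the primary outcome, use of any tobacco treatment, under the survey.

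**The concern.** An oversampled group has a higher chance of being in the sample than its population share warrants. To recover population rates, each member must count for less, in proportion to one over that chance. The written rule makes each member count for more. Followed literally, it gives rates further from the population than no weighting at all, in the one analysis the plan offers as representative.

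A second gap is that the plan does not say at which stage inclusion is counted or which population is the target. If enrolment or 6-month response differs by gender or race, a weight that stops at an earlier stage will not restore the population mix, even when correctly inverted.

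**Working it through.** **Inputs from the documents.** Up to 250 patients randomized 2:1, so about 167 and 83; invitation targets of 14% women and 24% minority patients; stated SEs of 3.9% and 5.4% (Power and Sample Size).

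**Assumptions.** The documents give no population shares, so these are shown as ranges: 5–10% women and 10–20% minority patients. The enrolled shares are set equal to the invitation targets for illustration.

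**The plan's own figure.** SE = √(p(1−p)/n). The plan states no p; the worst case p = 0.5 gives √(0.25/167) = 3.87%, which matches 3.9%. For the control arm, n = 83 gives 5.49% and n = 84 gives 5.45% against the stated 5.4%, a rounding-level gap that does not bear on this point.

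**Literal rule.** Let s be the sample share and q the population share. Relative inclusion probabilities are s/q for the group and (1−s)/(1−q) for the rest. With the probability as weight:

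weighted share = (s²/q) / [s²/q + (1−s)²/(1−q)]

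Women, s = 0.14, q = 0.07: 0.0196/0.07 = 0.280; 0.7396/0.93 = 0.795; share = 0.280/1.075 = 26.0%.

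| Group | Sample share | Assumed population share | Literal weights | Inverse weights |
|---|---|---|---|---|
| Women | 14% | 5% / 7% / 10% | 33.5% / 26.0% / 19.3% | 5% / 7% / 10% |
| Minority | 24% | 10% / 15% / 20% | 47.3% / 36.1% / 28.5% | 10% / 15% / 20% |

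The direction does not depend on q: whenever s > q, the literal rule pushes the share above s.

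**From shares to rates.** This needs an assumed difference in uptake. With women 7% of the population:

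- 40% in women, 20% in men: population 0.07×40 + 0.93×20 = 21.4%; unweighted 0.14×40 + 0.86×20 = 22.8%; literal 0.26×40 + 0.74×20 = 25.2%.
- 25% against 20%: population 20.35%; literal 21.3%, about 1 point higher.
- Equal uptake: no shift.

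**Stage of inclusion.** Suppose correct inverse weights used invitation probabilities only, and women enrolled at r times the rate of men. The weighted female share would be 0.07r/(0.07r + 0.93): 3.6% at r = 0.5, 7% at r = 1, 10.1% at r = 1.5. This shows why the stage matters, not which stage the plan uses.

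**Cost of correct weights.** The Kish design effect for one factor is q²/s + (1−q)²/(1−s).

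- Women, q = 5%: 0.0025/0.14 + 0.9025/0.86 = 1.067; q = 10%: 1.013.
- Minority, q = 10%: 0.01/0.24 + 0.81/0.76 = 1.107; q = 20%: 1.009.
- Both factors, if independent: from 1.013 × 1.009 = 1.02 to 1.067 × 1.107 = 1.18.
- Intervention-arm SE at 1.18: 3.87% × √1.18 = 4.2%.

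**Cell size.** If gender and race are independent, minority women at the targets number 250 × 0.14 × 0.24 = 8.4, of whom 2.8 would be in the control arm.

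**The case against.** The strongest reply is that the sentence fixes the direction itself. Only inverse weighting serves its stated aim, weighting by inclusion probabilities is common shorthand for inverse weighting, and no formula directs the opposite. That stands as a reading of intent. A reader might infer that the analysis will compound the oversampling; the documents do not show that. They show a rule that, taken at its word, defeats its purpose and that the analyst would have to correct unprompted.

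A reader might also infer that the probabilities cover invitation only, because the oversampling goal is set for patients invited. The documents do not support this. The Analysis Plan speaks of inclusion in the sample, which could equally mean the randomized sample. The stage is simply undefined.

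Nor are the pilot's main rates at risk. The weighting is additional, and the main estimates are not described as weighted. Randomization is stratified by race and gender, so balance between arms on these factors does not rest on the weights.

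Finally, large distortions in group share need not mean large distortions in rates. Even with uptake twice as high in women, the literal rule moves the rate by 25.2 − 21.4 = 3.8 points, about one SE of 3.87%, and the documents give no evidence that uptake differs by group. This limits importance; it does not remove the contradiction.

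**Conclusion.** The rule as written is wrong for its stated aim, most likely through loose wording, and should be corrected. The direction of the error is certain for any oversampled group; its size is not. It rests on assumed population shares, on enrolled shares equal to the invitation targets, and on a difference in uptake by gender or race. It touches only the supplementary population-weighted rates. The missing target population and stage of inclusion are a genuine gap, but a gap of definition. Correct weighting costs little precision: a design effect up to about 1.18 over the assumed ranges, treating the two factors as independent.

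**What to change.** Reword the rule along these lines: *each participant is weighted by the inverse of the probability of being in the analysed sample, according to gender and race.* Then:

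- **Name the target population.** For example, all patients eligible on the electronic record, or only those who would also pass the phone eligibility check. These differ, since the sponsor's earlier survey found 71% with text-capable phones.
- **Count inclusion to the sample analysed.** This runs through contact, eligibility and consent, and also 6-month response for survey outcomes. Enrolled over eligible is therefore not enough for the primary outcome.
- **Avoid sparse cells.** Weight to gender and race margins, or collapse cells, given about 8 minority women in all.
- **Report the weighted SE with its design effect.**

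The cost is a few sentences and counts by gender and race at each stage. These should be obtainable, since both variables already drive the oversampling and the stratification, although the documents do not say that the counts are kept. The weighted SE will be somewhat larger. Weights on gender and race cannot correct selection on other factors such as phone access, and the report should say so.
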